5.3.3 Actual Average Daily Dose (mg/day)

Actual average daily in main treatment period (mg/day) = Actual total cumulative dose in main treatment period (mg)/ Actual duration of study drug exposure in main treatment period (days)

Actual average daily in LTE treatment period (mg/day) = Actual total cumulative dose in LTE treatment period (mg)/ Actual duration of study drug exposure in LTE treatment period (days)

5.3.4 Study Drug Compliance (%)

Compliance with study drug will be calculated as the actual total cumulative dose (mg) taken divided by the planned number of doses (mg), i.e., do not adjust for missed doses, expressed as a percentage.

Compliance will be summarized by descriptive statistics for the main treatment period and LTE treatment period. The number and percentage of patients with 100% compliance, greater than 80% but less than 100% compliance and less than 80% compliance will be tabulated.

5.4 Efficacy Analyses

The ITT population will be used for all efficacy analyses. For analyses of a particular study drug dose level, all patients who received that dose at least once will be included.

Rescue medication is defined as any therapy used to rescue a patient (one of intravenous immunoglobulin [IVIG], high-dose steroids, platelet infusion or anti-D immunoglobulin infusion). A rescue therapy may be used if there is a significant safety event requiring 'rescue' from a deterioration in the patient's platelet count that in the opinion of the investigator puts the patient at significant risk of a safety event. Patients who take rescue while on study will be discontinued. Response status for patients who receive rescue therapy while on study will be evaluated using the platelet counts up until the time of rescue therapy.

The descriptive statistics for the main treatment period will be done by starting dose and overall for all study visits and by cycle of exposure (as appropriate), unless specified otherwise. All binomial confidence intervals for efficacy analyses will use the Clopper-Pearson method. Descriptive summary will be generated for data collected during the LTE period as needed. Patient data listings will be listed

by starting dose, patient, dose level and study visit, including both of the main treatment period and LTE period.

5.4.1 Primary Efficacy Endpoint

Platelet count is measured at visits as specified in the Schedule of Assessments (Table 3 to Table 6).

The primary efficacy endpoint is:

 Proportion of patients able to achieve two or more consecutive platelet counts, separated by at least 5 days, of ≥ 50,000/µL AND an increase of platelet count of ≥ 20,000/µL from baseline, by dose level, without use of rescue medication in the 4 weeks prior to the latest elevated platelet count.

The number and percentage of patients who meet the primary efficacy endpoint criteria in the main treatment period will be tabulated by dose level and overall. A 95% confidence interval will be calculated for the proportions using the Clopper-Pearson method. The response will be attributed to the dose level at the visit prior to the first of the two consecutive scheduled platelet counts occurred that are at least 5 days apart, see table below. A patient can have multiple responses within the same dose level and/or at different dose levels. This table will be repeated by starting dose.

Example 1: Patient had a response at 200 dose only			Example 2: Patient had a response at 200 and 400 doses.						
Visit	Dose	Platelets	Response	Dose that	Visit	Dose	Platelets	Response	Dose that
	dispensed			response is		dispensed			response is
	at this visit			attributed to		at this visit			attributed to
C1D1	200	25			C1D1	200	25		
C1D8	200	30		200	C1D8	200	30		200
C1D15	200	35		200	C1D15	200	35		200
C2D1	400	51	Υ	200	C2D1	400	51	Υ	200
C2D8	400	55		400	C2D8	400	55	Y	400
C2D15	400	42		400	C2D15	400	53		400
C3D1	600	39		400	C3D1	600	39		400
C3D8	600	40		600	C3D8	600	40		600
C3D15	600	41		600	C3D15	600	41		600
Example 3: Patient had a response at 200 and 600 doses.			Example 4: Patient had a response at 200, 400 and 600 doses.						
Visit	Dose	Platelets	Response	Dose that	Visit	Dose	Platelets	Response	Dose that
	dispensed			response is		dispensed			response is
	at this visit			attributed to		at this visit			attributed to
C1D1	200	25			C1D1	200	25		
C1D8	200	30		200	C1D8	200	30		200
C1D15	200	35		200	C1D15	200	35		200
C2D1	400	51	Υ	200	C2D1	400	51	Υ	200
C2D8	400	55		400	C2D8	400	55	Υ	400
C2D15	400	42		400	C2D15	400	53		400
C3D1	600	43		400	C3D1	600	39		400
C3D8	600	59	Υ	600	C3D8	600	59	Υ	600
C3D15	600	59		600	C3D15	600	59		600

Time-series graphs will be provided for platelet counts over the duration of the study for each patient. This individual platelet profile will distinguish main, LTE and FU period, display the dose levels the

patient received, and indicate the clinically relevant responding platelet levels and when the patient received rescue therapy.

Descriptive summary will be generated for the main and LTE period.

Graphical presentation of the results (i.e., spaghetti plot, line plot, etc.) may also be explored. Depending on the impacts of Covid-19, sensitivity analyses on the primary endpoint may be performed.

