#### Benefit assessment

Patients with ITP were expected to only transiently benefit from rilzabrutinib with the initial dose escalation scheme and 12-weeks of treatment, although anecdotal evidence from the Phase 2 study of rilzabrutinib in pemphigus suggests a durable effect post-treatment may occur in some patients. The additional non-clinical data supported longer treatment durations enabling amending to 24 weeks of treatment and allowing dose escalation to the highest dose level, as well as an LTE for patients with platelet response.

Preliminary review of the efficacy data in Part A of this study demonstrated a dose response and that patients with ITP who failed multiple treatments were able to achieve a fast and durable platelet response at the 400 mg BID dose of rilzabrutinib. Patients treated with once daily doses were less likely to achieve fast platelet response and the primary endpoint (10). This evidence of

treatment effect supports initiation of Part B of the study that will focus on further investigating this dose of rilzabrutinib in this patient population. Preliminary results of Part A and Part B provide evidence that treatment with rilzabrutinib 400 mg BID induces a rapid and durable platelet response and continued to be well tolerated in patients with ITP (11, 12).

**Benefit-risk:** To date, preliminary analyses of efficacy and safety in patients with ITP support an overall favorable benefit-risk profile, and to continue the development of rilzabrutinib for patients with ITP.

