## 3.1.2 Efficacy Objectives

- To explore the clinical activity of up to four dose levels of rilzabrutinib in relapsed/refractory patients with ITP
- To identify a potential dose regimen to use in future studies of rilzabrutinib in patients with ITP

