# 4 INVESTIGATIONAL PLAN

# 4.1 Overall Study Design and Plan Part A

This is an adaptive, open-label, dose-finding study of rilzabrutinib in patients with ITP who are refractory or relapsed with no available and approved therapeutic options, with a platelet count  $<30,000/\mu L$  on two counts no sooner than 7 days apart in the 15 days before treatment begins.

15 May 2024

Version number: 1

The active treatment period is 24 weeks and the post-treatment follow up period is 4 weeks.

Once a patient escalates to the 400 mg BID dose in the active treatment period, the patient will stay at this dose for 24 weeks.

Each patient is enrolled in the study and allowed to up-titrate their dose after 28 days of rilzabrutinib therapy at each dose level if they do not experience a platelet response (as defined in the primary endpoint) or a DLT at the last dose level. If they experience a platelet response in the first cycle at any one dose level but do not have a platelet response in the second cycle at that dose, they may dose escalate at the end of the second cycle. Patients experiencing a platelet response (as defined for the primary endpoint) will not have their dose escalated at the next cycle.

The "sentinel cohorts" at each dose level consist of the first 3 patients, or 6, if 3 extra are added for a DLT or platelet response (as defined in the primary endpoint and sustained for at least 3 of 4 consecutive platelet counts at any dose level). To be evaluable in a sentinel cohort, patients must have ≥75% compliance over the 28-day dosing period. The sentinel cohort data is reviewed by the IDSM, in order to choose the starting dose for additional, new patients entering the study. After review, the IDSM may determine that a starting dose for new patients should be dropped for futility (lack of platelet response), increased to the next planned dosing level, kept the same or reduced (Section 4.4).

Doses levels will be: 200 mg QD; 400 mg QD; 600 mg per day (300 mg BID); 800 mg per day (400 mg BID) (see table below). Due to the design, not all patients will necessarily be dosed at all dose levels.

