# 4.4 Dose Escalation Rules Part A Only

### Individual:

- Patients will dose-escalate to successive dose levels unless they are withdrawn, have a platelet response at the current dose level, or the next dose level has been determined to be ineligible for further enrollment (see Maximal Administered Dose [MAD], below)
- Patients experiencing a platelet response (as defined for the primary endpoint) will not have their dose escalated at the next cycle. If they do not experience a platelet response during the second cycle of the same dose level they may dose escalate for the following cycle. If they require rescue medication subsequently because the platelet response was only transient, these patients will be discontinued from the study.

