# 4.8 Study Duration and Duration of Patient Participation

# Part A:

Patients will receive rilzabrutinib treatment for 24 weeks, starting on Day 1 and ending on Study Day 169, followed by 4 weeks of post-treatment safety follow-up. The expected study duration is approximately 18 months from the first patient treated to the last patient completing, and approximately 32 weeks per patient.

Patients who are dose escalated to 400 mg BID will continue in the active treatment period until 24 weeks of treatment at the 400 mg BID dose is completed.

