# **10.5** Determination of Sample Size

### Part A

The sample size for this study is based on clinical considerations. Assuming an expected efficacy rate for the primary endpoint of 40% (platelet response), with 15 evaluable patients there will be 80% confidence that the true proportion will be 24% and above ( $80 \pm 16\%$  confidence interval [CI]) using normal approximation methods.

The results from this study will be used to

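### The Part A by-dose primary table counts response over about 4 weeks at the lower doses and up to 24 weeks at 400 mg BID, so it cannot separate dose from time on dose and selection

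*SAP*

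**What the plan says.** Part A is dose-finding. One of its efficacy objectives (Protocol 3.1.2) reads: "To identify a potential dose regimen to use in future studies of rilzabrutinib in patients with ITP".

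Dose rises within patient. Under Protocol 4.1 patients are "allowed to up-titrate their dose after 28 days of rilzabrutinib therapy at each dose level if they do not experience a platelet response", and Protocol 4.4 makes escalation the default: "Patients will dose-escalate to successive dose levels unless they are withdrawn, have a platelet response at the current dose level". At the top level the rule changes. Under Protocol 4.8 a patient who reaches 400 mg BID by escalation "will continue in the active treatment period until 24 weeks of treatment at the 400 mg BID dose is completed".

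Part A SAP 5.4.1 then specifies that counts and shares of "patients who meet the primary efficacy endpoint criteria in the main treatment period will be tabulated by dose level and overall", with Clopper-Pearson intervals and a repeat by starting dose. Response means one pair of consecutive qualifying counts at least 5 days apart, credited to the dose in force before the first count of the pair. SAP 5.4 puts everyone who ever received a dose in that dose's denominator. No common observation window is set for the comparison.

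**The concern.** An endpoint of the 'ever achieved' kind has a rate that grows with the time observed. Here that time is tied to dose by design: short at the three lower levels for anyone not responding, long at the top level. A second distortion runs the other way. Patients arriving at 400 mg BID by escalation have already failed to respond lower down, so they are depleted of easy responders, yet they share a column with patients who started there.

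The by-dose table is the primary efficacy display in a study meant to identify a regimen. A contrast between its columns could reflect dose, weeks of opportunity or selection, and the table gives the reader no means of telling which.

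**Working it through.** **The plan's own figure.** Protocol 10.5 starts from this premise: "Assuming an expected efficacy rate for the primary endpoint of 40% (platelet response), with 15 evaluable patients". The section then concludes that "there will be 80% confidence that the true proportion will be 24% and above". The normal-approximation 80% interval gives 0.40 − 1.2816 × √(0.40 × 0.60/15) = 0.40 − 0.162 = 0.238, so the 24% reproduces. It concerns one proportion and says nothing about comparing doses. I borrow its 40% below as an assumed 24-week response rate.

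**Windows.** A non-responder has 4 weeks at each lower dose. Weeks at 400 mg BID, by starting cohort (200 QD / 400 QD / 300 BID / 400 BID), from Part A SAP 2.2, Tables 1 and 2, and footnote 16 of Table 4:

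| Protocol version | Weeks at 400 mg BID |
|---|---|
| 7 (12 weeks in total) | 0 / 4 / 8 / 12 |
| 8 (24 weeks in total) | 12 / 16 / 20 / 24 |
| 9 onward | 24 / 24 / 24 / 24 |

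**No dose effect, constant hazard.** With p(w) = 1 − 0.60^(w/24), the rates at 4, 8, 12, 16, 20 and 24 weeks are 8.2, 15.7, 22.5, 28.9, 34.7 and 40.0%. Each lower-dose column shows 8.2%. With equal starting cohorts (an assumption; the documents give no split), the share of a cohort reaching 400 mg BID is 0.918 per lower dose passed: 1, 0.918, 0.843 and 0.774. The 400 mg BID column is then:

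- Version 9 onward: everyone has 24 weeks, so 40%.
- Version 8: (1 × 0.400 + 0.918 × 0.347 + 0.843 × 0.289 + 0.774 × 0.225) / 3.535 = 1.136/3.535 = 32%.
- Version 7: (1 × 0.225 + 0.918 × 0.157 + 0.843 × 0.082) / 2.761 = 0.438/2.761 = 16%.

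**No dose effect, fast onset.** Suppose 40% of patients can respond, with exponential onset of median 2 weeks, equal cohorts and version 9 windows. At 200 mg QD the rate is 0.40 × (1 − 0.5²) = 30%. At 400 mg BID, starters contribute 0.400 responders per patient. The escalated groups contribute 0.100, 0.025 and 0.006 responders from 0.700, 0.625 and 0.606 patients. The column is 0.531/2.931 = 18%, below the 30% at 200 mg QD. It blends about 40% among starters with 0.131/1.931 = 7% among escalated patients.

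**Other no-dose-effect patterns** (simulated, version 9 windows; onset and cohort splits are assumptions):

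| Assumption | 200 QD / 400 QD / 300 BID / 400 BID, % |
|---|---|
| 40% can respond, median onset 8 weeks, equal cohorts | 12 / 11 / 10 / 26 |
| Median 4 weeks | 20 / 17 / 14 / 23 |
| Median 2 weeks | 30 / 22 / 17 / 18 |
| Median 1 week | 38 / 25 / 18 / 15 |
| Median 2 weeks, 70% starting at 400 mg BID | 30 / 22 / 17 / 33 |
| Median 1 week, 70% starting at 400 mg BID | 37 / 25 / 18 / 32 |
| Gamma frailty, variance 1, equal cohorts | 10 / 10 / 9 / 37 |
| Gamma frailty, variance 4, equal cohorts | 17 / 14 / 12 / 30 |

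Where an excess appears it is a step at 400 mg BID; the three lower doses are flat or falling.

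**The starting-dose repeat.** If it counts response at any dose, the constant-hazard null gives 40/40/40/40% under version 8. Under version 9 onward total time is 36/32/28/24 weeks, so p(w) gives 54/49/45/40%, a tilt against starting at 400 mg BID. If it splits dose levels within each starting cohort, the unequal windows remain.

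**The case against.** The SAP tests no hypothesis (3.8) and offers other views of the data: the starting-dose repeat, the share of weeks at or above 50,000/µL, summaries by cycle of exposure (3.4.4) and individual profiles showing dose. These are genuine partial safeguards, but none equalises the window for the primary endpoint. The starting-dose repeat behaves as worked out above. The share-of-weeks endpoint normalises for time but is a different endpoint; moreover, the title of 5.4.2.1 promises results by dose level while its text summarises across all levels. The cycle-of-exposure mapping serves descriptive visit summaries, not the responder proportion. Leaving out tests does not remove bias from a descriptive contrast.

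A reader might also infer that 400 mg BID was chosen from this table. Protocol 2.2 does report a dose response and says: "Patients treated with once daily doses were less likely to achieve fast platelet response and the primary endpoint". But that is a preliminary review citing a 2019 meeting presentation whose tables and windows are not in these documents. Part B, with 400 mg BID as the selected dose, entered in protocol version 13 (5 March 2020), before Part A SAP version 1.0 (4 November 2020). The sentinel reviews that set starting doses used one or two 28-day cycles (Protocol 2.1), so they do not share the 4-versus-24-week gap. That part of the objection stands: the point concerns how the table may be read, not how the dose was chosen.

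**Conclusion.** The point holds as a defect of comparability. The by-dose primary table confounds dose with time on dose and with selection. Under a constant-hazard null with equal cohorts, the 400 mg BID column exceeds each lower dose about 5-fold under version 9 onward (40/8.2), 4-fold under version 8 (32/8.2) and 2-fold under version 7 (16/8.2).

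Two stronger readings are not supported. One is that the table must show a dose response when dose has no effect: with a median onset of 2 weeks or less and equal cohorts, the excess disappears or reverses, and the documents themselves expect rapid effect (Protocol 2.1.1). The other is that all Part A patients had 24 weeks at 400 mg BID: that is the version 9 rule, and under version 8 it applies only to patients starting there.

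The windows come from the documents. Response rates, onset times, frailty and cohort splits are assumptions, so the size and even the direction of the bias in the actual data are unknown. The added analysis is advisable, not critical.

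**What to change.** In Part A SAP 5.4.1, add a supportive table by starting dose with Clopper-Pearson intervals. Count a patient as a responder if the first count of a qualifying pair falls from Day 8 through the pre-dose count on Day 1 of the next cycle, with the next scheduled count as confirmation.

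This keeps the existing attribution rule. Requiring both counts inside the first 28 days would turn the SAP's own Example 1 (51 on C2D1, then 55 on C2D8, credited to the 200 mg dose) into a non-response. Because SAP 3.4.4 maps only Days 1, 8, 15 and 22 to a cycle, the text must state that the next-cycle Day 1 count is used. A pair starting on that day is confirmed after any dose change, as under the current rule.

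Label the whole-period by-dose table as descriptive and not exposure-adjusted, and footnote it with median (range) weeks on each dose level.

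The cost is one table and one footnote from data already collected. The Part B SAP (1.1) says a Part A study report has been prepared, so the table should be identified as an addition. Its limits are real. Lower starting-dose cells hold about 3 to 6 patients, giving intervals such as 0 to 71% for 0/3 or 0.4 to 64% for 1/6, and late responders are not counted. It should support, not alone decide, any comparison of doses.

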			On-treatment clinic visits, treatment cycles of 28days, X≤6 ¹⁶					Early
	Screening (D-28 to D-1)	C1D1 only	CXD1 (first day of each cycle) ¹³	CXD15	D169 (last day of active rilzabrutinib (PRN1008) treatment)	End of Study D197	Weekly lab visit between clinic visits ¹⁴	Withdrawal/ Unscheduled visit
	,	,	,,,,,		,			
ITP-BAT Bleeding Scale ¹²	Х		X	Х	X	Х		X

- 1. Clinic/laboratory visit windows are ± 3 days for all dosing period and lab visits. Labs to confirm eligibility prior to Cycle 1 Day 1 may be taken up to 3 days in advance of Cycle 1 Day 1.
- 2. See protocol section 4.3 of the protocol dose-escalation rules
- 3. Full physical examination at screening, abbreviated physical examination at other visits.
- 4. Triplicate ECG pre-dose and at 2 hours post-dose (± 15 minutes) on the first day of dosing at each new dose level. Where patients are continuing into a new cycle at the prior dose level, ECG is not required.
- 5. For women of childbearing potential only. Serum pregnancy tests are performed at screening, urine pregnancy tests are performed at other visits.
- 6. To confirm postmenopausal status for women who are not surgically sterile and of reproductive potential
- 7. T/B/NK/monocyte counts (i.e., CD3, CD4, CD8, CD14, CD19, CD16/56), and B cell subsets (i.e., naïve, memory and plasmablasts)
- 10. On Day 1 of each new dose level cycle, patients will take their dose in the clinic and remain in the clinic for intensive PK sampling for 6 hours following the first dose at time points: 0, 0.5, 1, 1.5, 2 (time windows for first 2 hours are ± 2 minutes), 3, 4, and 6 hr (time windows for > 2 hr samples are ±5 minutes). On subsequent clinic visits of each dosing cycle, patient should take their dose in the morning before the clinic visit (whether dosing is QD or BID), and the PK sample is taken at random times after last dose (with time of last dose recorded on CRF, no time window). Where patients are continuing into a new cycle at the prior dose level, PK sampling is not required.
- 11. If still taking rilzabrutinib (PRN1008)
- 12. ITP-BAT scale performed at all clinic visits but not laboratory-only visits
- 13. Assessments on Day 1 of each 28-day treatment Cycle are performed pre-dose; ECGs and PK samples are also collected at additional times post-dose per Footnote 4 (ECGs) and Footnote 10 (PK samples).

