3.3 Treatment Groups

3.3.1 Treatment Group Labels

The following treatment group labels will be used in the tables, listings and figures:

Treatment Group Label	Patients Included
Overall	All patients in the population will be included in this group.
Starting Dose 200 mg QD	Patients will be classified to these groups according to the starting
Starting Dose 400 mg QD	dose received. Each patient will be assigned to only one of these
Starting Dose 300 mg BID	groups.
Starting Dose 400 mg BID	
200 mg QD	Patients are evaluable in the dose group(s) if the dose level was
400 mg QD	received during the defined period (Sections 3.4.1and 3.5.2). Since
300 mg BID	most patients received more than one dose, a given patient can be
400 mg BID	assigned to multiple dose levels.
	For each of the following type of analyses, patients will be classified to
	each dose level based on:

Treatment Group Label	Patients Included
	 Dose level received prior to the visit for responder analyses, time-to analyses and analyses of proportion of patients meeting an endpoint, i.e., percent of weeks with platelet counts ≥ 50,000/μL. Dose level received at the onset of event for adverse events, and bleeding events analyses. Adverse events started after date of last dose of study drug will be attributed to the last dose level received. Dose level received during the time the medication was taken for any medication analyses. Medications taken after date of last dose of study drug will be attributed to the last dose level received.

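### Part A by-dose response rates below 400 mg BID can include responses confirmed only after escalation, and no sensitivity table shows how many

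*SAP*

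**What the plan says.** The Part A primary endpoint (Protocol 3.3.2 and 10.2; SAP Part A 4.1 and 5.4.1) requires two or more consecutive counts of at least 50,000/µL, at least 5 days apart and at least 20,000/µL above baseline, reported by dose level. The protocol does not say which dose is credited when the two counts fall on either side of a dose change.

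The SAP supplies a rule. Section 5.4.1: "The response will be attributed to the dose level at the visit prior to the first of the two consecutive scheduled platelet counts". Section 3.3.1 agrees: "Dose level received prior to the visit for responder analyses". Section 5.4.1 adds: "A patient can have multiple responses within the same dose level and/or at different dose levels". The denominator is set in SAP 5.4: "For analyses of a particular study drug dose level, all patients who received that dose at least once will be included". Four worked examples follow; the first is labelled "Example 1: Patient had a response at 200 dose only".

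Protocol 4.1 allows escalation after 28 days "if they do not experience a platelet response (as defined in the primary endpoint) or a DLT at the last dose level", and Protocol 4.4 says: "Patients experiencing a platelet response (as defined for the primary endpoint) will not have their dose escalated at the next cycle". On timing, a footnote to the schedules in SAP 2.7 says: "Assessments on Day 1 of each 28-day treatment Cycle are performed pre-dose".

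The only sensitivity analysis that SAP 5.4.1 mentions for the primary endpoint concerns Covid-19. None addresses attribution.

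**The concern.** A single qualifying count is not a response; the confirming count makes it one. In Example 1 the first qualifying count is at C2D1, before the first 400 mg dose, and the confirming count is at C2D8, about a week into 400 mg. The table's own last column attributes the C2D8 count to 400, yet the response is credited to 200 alone. At the time of escalation this patient had no confirmed response at 200 mg; the primary table shows a responder at 200 mg.

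The effect has one direction under escalation. Each dose below the top can draw a confirming count from the dose above, while 400 mg BID has none above it. If the higher dose works better, the lower-dose rates rise and the differences between doses shrink. The endpoint is defined by dose level, and identifying a dose regimen is a stated Part A objective, so a reader will use these rates for that comparison.

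**Working it through.** **1. Reproduce the SAP's examples.** Inputs: the visits, doses and counts tabulated in SAP 5.4.1. Baseline is taken as the C1D1 value of 25 (thousand/µL). This is an assumption, because SAP 3.4.5 also averages in two screening counts that the examples do not show. Each count belongs to the dose dispensed at the preceding visit. The pair C2D1 = 51 and C2D8 = 55 occurs in all four examples. Both counts are at least 50, the rises are 51 − 25 = 26 and 55 − 25 = 30, and the visits are 7 days apart.

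| Example | Qualifying pairs (dose of first / second count) | Credited under SAP rule | Credited if both counts must be on one dose |
|---|---|---|---|
| 1 | C2D1/C2D8 (200/400) | 200 | none |
| 2 | C2D1/C2D8 (200/400); C2D8/C2D15 (400/400) | 200, 400 | 400 |
| 3 | C2D1/C2D8 (200/400); C3D8/C3D15 (600/600) | 200, 600 | 600 |
| 4 | C2D1/C2D8 (200/400); C2D8/C2D15 (400/400); C3D8/C3D15 (600/600) | 200, 400, 600 | 400, 600 |

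The third column matches the SAP in every example. The 200 mg credit appears in 4 of 4 and always rests on the straddling pair; under the same-dose rule it appears in 0 of 4. All four patients remain overall responders either way, provided the overall endpoint does not require both counts on one dose. The examples omit the scheduled Day 22 counts and are illustrations, so 4 of 4 is not an estimate of frequency.

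**2. Possible size (assumed scenario).** In a 28-day cycle, four weekly counts are attributed to the lower dose: Days 8, 15 and 22 and the next cycle's pre-dose Day 1. They form three within-dose pairs and one pair that straddles escalation. Let each count qualify independently, with probability p on the lower dose and r on the next, and let q = 1 − p. The documents give neither p nor r.

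- Within-dose response: W = 1 − (q⁴ + 4pq³ + 3p²q²).
- Added by the straddling pair: S = p·q·(1 − p²)·r, meaning no pair so far, third count not qualifying, fourth qualifying, next count qualifying.
- Credited to the lower dose: W + S.

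With p = 0.10: W = 1 − (0.6561 + 0.2916 + 0.0243) = 0.0280, and p·q·(1 − p²) = 0.1 × 0.9 × 0.99 = 0.0891.

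- r = 0.10 (no dose effect): 0.0280 + 0.0089 = 3.7%.
- r = 0.40: 0.0280 + 0.0356 = 6.4%.
- r = 0.50: 0.0280 + 0.0446 = 7.3%.

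Measured against the no-dose-effect case, the share due to the higher dose is (6.36 − 3.69)/6.36 = 42% at r = 0.40 and (7.26 − 3.69)/7.26 = 49% at r = 0.50.

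With p = 0.20 and r = 0.50: W = 1 − (0.4096 + 0.4096 + 0.0768) = 10.4%; S = 0.2 × 0.8 × 0.96 × 0.5 = 7.7%; credited 18.1%. With r = 0.20 the credited rate is 10.4 + 3.1 = 13.5%, so the share due to the higher dose is (18.08 − 13.47)/18.08 = 25%.

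**3. Effect of one straddling response on a small group.** Clopper-Pearson 95% intervals, with group sizes assumed. In a group of 6, 0/6 (0%, 0 to 45.9%) becomes 1/6 (16.7%, 0.4 to 64.1%). In a group of 15, 0/15 (0%, 0 to 21.8%) becomes 1/15 (6.7%, 0.2 to 31.9%).

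**The case against.** The strongest defence is that this is a prespecified convention filling a gap in the protocol. It is stated in two SAP sections and illustrated four times. Attribution by onset is defensible because the first qualifying count is taken pre-dose and was reached wholly on the lower dose. This stands, and it is why the rule need not be replaced.

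A reader might infer that the lower dose did not produce these responses because the protocol escalated the patient. The documents do not support that. The escalation rule is a real-time decision: at C2D1 the confirming count does not yet exist. It shows only that no response had been confirmed, and some straddling pairs would have been confirmed on the lower dose anyway.

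A reader might also infer that the choice of 400 mg BID was distorted. The chronology is against it. SAP Part A 2.5 and 2.6 place Part B, at the selected dose, in protocol version 13.0 of 05 Mar 2020, whereas the Part A SAP versions are dated 04 Nov 2020 and 03 Mar 2021. Starting-dose decisions used sentinel-cohort toxicities and sustained responses, not this table. Flattening would also work against the selected dose.

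Finally, a reader might treat every straddling pair as taken from the higher dose. In the 10% scenarios that gives 3.56/6.36 = 56% to 4.46/7.26 = 61% of credited responses. It ignores that a fourth pair adds responses even when the doses are equal.

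There are partial safeguards: the table is repeated by starting dose, individual profiles display dose levels, and no hypothesis is tested. None of them tells the reader how many by-dose responses were confirmed on the next dose.

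**Conclusion.** The point holds in a limited form. By-dose rates below 400 mg BID can include responses confirmed only after about a week on the next dose, and the plan has no analysis that shows how many. The likely effect is higher lower-dose rates and a flatter by-dose comparison. Only pairs that straddle an escalation are affected. The overall rate is not, nor are patients who start at 400 mg BID.

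The size is unknown. In the assumed 10% scenarios a within-dose 2.8% becomes 6.4% to 7.3%, with 3.7% expected from the extra pair alone. These figures rest on independent weekly counts and on probabilities that the documents do not give. The attribution rule is not an error, and the documents do not show that it affected dose selection.

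**What to change.** Keep the onset rule as the prespecified primary analysis. Add one by-dose sensitivity table that credits a dose only when both qualifying counts are attributed to it. For each dose, show the number of straddling pairs separately and count them in the overall rate. State that the by-dose comparison is to be interpreted from both tables.

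The existing data suffice. SAP Part B 1.1 says that the Part A main period is complete and its study report has been prepared, so this would be a supplementary table. Its limitation should be stated: the same-dose rule under-credits a true lower-dose response first seen at the last visit before escalation, and a patient like the one in Example 1 becomes an overall responder at no single dose. The two tables therefore lean in opposite directions.

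The credited doses in the four examples follow the stated rule and need no correction. Separately, Examples 2 and 4 show a move to 600 at C3D1 after a response credited to 400 in the cycle just ended (55, then 53). That does not agree with the escalation rule in Protocol 4.1 and 4.4, and the passages must be reconciled.
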